5.4. Continuing Eligibility Criteria

Subjects may enter the Open-Label Extension if the subject:

- **has not withdrawn consent for the study**
- **has no new infections that, in the judgment of the investigator, would preclude addition of a new immunosuppressive or immunomodulatory treatment**
- **has had no requirement for the addition of new immunosuppressive treatment during the prior 12 weeks and no anticipated requirement during the next 12 weeks.**

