4. STUDY DESIGN

This study will evaluate the efficacy, safety, tolerability, and pharmacokinetics of up to 12 weeks of treatment with each of three dose regimens of CCX140-B or placebo, when used in combination with stable standard of care therapy in subjects with FSGS with significant proteinuria, assessed as $UPCR \geq 1g/g$ at Screening. Following the 12-week blinded treatment period, **the study will evaluate up to 24 weeks of treatment with CCX140-B: all subjects who remain eligible** will receive active treatment for an additional 12 weeks to assess safety and durability of effect.

The target is to enroll 40 male or female subjects in this randomized, double-blind, placebo-controlled, Phase 2 study. Randomization will be stratified by **UPCR <3.5 g protein/g creatinine versus UPCR ≥3.5 g protein/g creatinine at baseline using the screening UPCR** and by the use of glucocorticoids and/or immunosuppressive medications (yes, no).

Subjects will be randomized 1:1:1:1 to one of four treatment groups:

- Group A: Placebo (N=10)
- Group B: CCX140-B 5 mg once daily (N=10)
- Group C: CCX140-B 10 mg twice daily (N=10)
- Group D: CCX140-B 15 mg twice daily (N=10)

Study medication will be taken by the subjects for 84 days, as follows:

- Group A: Three placebo tablets, taken twice daily;
- Group B: One 5 mg CCX140-B tablet and two placebo tablets in the morning; three placebo tablets in the evening;
- Group C: Two 5 mg CCX140-B tablets and one placebo tablet, taken twice daily
- Group D: Three 5 mg CCX140-B tablets, taken twice daily

All subjects will take blinded **oral** study medication **twice daily, 3 tablets** in the morning and **3 tablets in the evening**, with or without food, for **12 weeks** (84 consecutive days). Following the 84-day blinded dosing period, all subjects **who remain eligible** will take open label CCX140-B for an additional **12 weeks** (84 consecutive days) at the highest **tolerated** dose under evaluation, currently planned to be 15 mg twice daily. **The decision on the dose for the open-label period will be made** by the Sponsor, with the advice of the unblinded Data Monitoring Committee (DMC). **After completion of treatment for whatever reason, including early termination**, all subjects are expected to return at 2, 7 and 14 days after taking the last dose of study medication **for assessment of elimination phase PK and 28 days after taking the last dose of study medication for PK and safety monitoring**.

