- The AIDS Clinical Trials Group Brief Peripheral Neuropathy Screening Tool Brief Peripheral Neuropathy Screening Tool (ACTG-BPNST) to assess early evidence of neuropathy;
- Monitoring for adverse events of infection;
- Alkaline phosphatase, ALT, AST and bilirubin (**total and direct**); to assess for evidence of drug induced liver injury.

For assessment of pharmacokinetics, study procedures will include

- Seven blood samples collected over 6 hours on Study Day 1 and at steady state (Study Day 15, or within 2 weeks thereafter) to assess AUC_{0-6} following the first administration of study drug, and at steady state;
- Assessment of C_{min} at intervals to ensure that exposure is within the projected range, with adequate safety margin based on the NOAEL established in preclinical toxicology;
- Upon discontinuation of treatment for any reason, collection of blood at 2 days, 7 days and 14 days following discontinuation to assess elimination.

All study procedures are presented in the [Time and Events table](#).

Subjects who are using an angiotensin converting enzyme (ACE) inhibitor, angiotensin receptor blocker (ARB) or other blocker of the renin angiotensin aldosterone system (RAAS), or who are using glucocorticoids, a calcineurin inhibitor or other immunomodulatory or immunosuppressive

[figure not shown]
therapy, should be on a stable dose for at least 4 weeks prior to screening. The dose of these medications must be kept constant over the course of the study in order to prevent undue influence of changes in these medications on the efficacy and safety assessments except when adjustment is required for patient well-being. The investigator must also attempt to keep doses of other medications, and lipid-lowering medications fixed throughout the blinded study period in order to prevent undue influence of changes in these medications on the efficacy and safety assessments.

Subjects who experience deteriorating renal function based on an increase in serum creatinine of at least 50% (confirmed by a repeat measurement after 2 weeks) which is otherwise not explained (e.g., dehydration, new medication), or increase in UPCR of >3.0 g/g (confirmed by a repeat measurement after 2 weeks) during the 12-week treatment period, will exit the treatment phase of the study and be treated at the discretion of the treating physician. All subjects who discontinue treatment will remain in the study for follow up and outcome recording.

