4.2. Dose Modification Guidelines

The DMC will be responsible for reviewing safety data throughout the course of the study. In the event the DMC has a strong indication that there are significant dose-related adverse events the DMC can make the recommendation to discontinue enrollment to the affected arm and to step-down all subjects to the next lower dose arm. In addition to the planned data reviews, the DMC charter will include pre-specified rules that trigger an Ad Hoc review of data by un-blinded treatment group.

Subjects participating in the Open-Label Extension will be switched over to the highest safest dose of the CCX140-B.

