4.2.1. Stopping Guidelines

An independent Data Monitoring Committee (DMC) will be responsible for reviewing safety data throughout the course of the study. Among other responsibilities, the DMC is tasked with implementing dose modification guidelines to assure the safety of all study participants.

Guidelines will be defined for stopping the study, halting enrollment or halting treatment based on safety events occurring in more than 1 subject. General dose modification guidelines for individuals are provided below.

Table 2: Dose Modification Guidelines for Single Subjects

| Assessment | Event | Timing | Response |
|---------------------------------------|---|--|-------------------------------------|
| Serum Creatinine | 50% increase from baseline value | If confirmed by repeat measurement after 2 weeks | Discontinue treatment with CCX140-B |
| Urine Protein:Creatinine ratio (UPCR) | If baseline UPCR < 6.0 g/g an increase of >3.0 g/g; if UPCR \geq 6.0 g/g an increase of 50% | If confirmed by repeat measurement after 2 weeks | Discontinue treatment with CCX140-B |

| Assessment | Event | Timing | Response |
|-----------------------------------|--|--|--|
| ALT, AST | ALT or AST ≥ 8 x ULN | Retest within 72 hours (ALT, ASP, ALP and Total Bilirubin should all be re-tested) | If confirmed, discontinue treatment with CCX140-B |
| ALT, AST | ALT or AST ≥ 5 x ULN for more than 2 weeks | Retest within 72 hours and then 2-3 times per week (ALT, ASP, ALP and Total Bilirubin should all be re-tested) | If confirmed, discontinue treatment with CCX140-B |
| ALT, AST, Total Bilirubin and INR | ALT or AST ≥ 3 x ULN and either Total Bilirubin > 2 ULN or INR > 1.5 | Retest within 72 hours (ALT, ASP, ALP, Total Bilirubin and INR should all be re-tested) | If confirmed, discontinue treatment with CCX140-B |
| ALT, AST | ALT or AST ≥ 3 x ULN with the appearance of fatigue, nausea, vomiting, right upper quadrant pain or tenderness, fever, rash and /or eosinophilia ($>5\%$) | | Discontinue treatment with CCX140-B |
| LDH | LDH ≥ 2 times upper limit of normal, and confirmed to not be related to specimen handling | Halt treatment then reassess after 2 weeks | If within normal range, continue to treat at reduced dose, defined as the next lower dose. Otherwise, contact Medical Monitor to discuss next steps |

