- The date and time of the last dose of CCX140-B or placebo prior to collection of the PK sample will be recorded
- Blood samples will be collected before dose administration for serum chemistry (including coagulation panel and lipids), hematology, serum pregnancy test (in women of childbearing potential), PK (time 0 only), plasma MCP-1, and PD (including lymphocyte subset) measurements; record the time of blood collection
- **Process the first morning void urine sample collection for quantitative urinalysis, UPCR, UACR, Cystatin C, Urine MCP-1, MCP-1/creatinine ratio and urine PD assessments**
- **Process the 24-hour urine sample collection for quantitative urinalysis, UPCR, UACR, Cystatin C, Urine MCP-1, MCP-1/creatinine ratio, urine PD assessment, and urine protein excretion/day**
- Subjects will be asked to complete the SF-36 v2 and EQ-5D-5L.
- The ACTG Brief Peripheral Screening Tool will be administered
- If the subject has not yet taken the morning dose of CCX140-B/placebo for this day, the subject will be asked to take the dose
- Drug accountability and reconciliation with subject completed diaries

- All study drug medication containers must be returned and drug usage must be reconciled against the completed diaries since continuing subjects will be given new drug supply of active study medication for open label dosing.
- Any changes in concomitant medication use will be recorded
- Any adverse events will be recorded
- **Assessment of continuing eligibility requirements:**
 - **has not withdrawn consent for the study**
 - **has no new infections that in the judgment of the investigator would preclude addition of a new immunosuppressive or immunomodulatory treatment**
 - **has had no requirement for the addition of new immunosuppressive treatment during the prior 12 weeks and no anticipated requirement during the next 12 weeks**
- **Provide the subject with the kit for collection of the first morning void**
- After all study procedures have been completed, **discontinuing subjects** will be reminded to:
 - **come to the study center at 2 days, 7 days and 14 days after the last dose for PK elimination and**
 - **come to the study center for the Week 16 follow-up visit**
- **Continuing subjects will be reminded to:**
 - Complete their diary each day immediately after each dose
 - Come to the study center for the Week 13 study visit, before taking the dose of **study drug**

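### Extension entry and dosing rules do not refer to Table 2, so a subject dose-reduced for a safety event gets conflicting instructions at Week 12

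*Protocol*

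**What the plan says.** **Entry.** Protocol 5.4 states "Subjects may enter the Open-Label Extension if the subject" and lists three conditions. The first two are "has not withdrawn consent for the study" and "has no new infections that, in the judgment of the investigator, would preclude addition of a new immunosuppressive or immunomodulatory treatment". The third is that no new immunosuppressive was needed in the previous 12 weeks and none is expected in the next 12. Section 7.7 repeats the list at Week 12 under "Assessment of continuing eligibility requirements". Footnote 6 of the Time and Events Table has the same content but presents it as a minimum.

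**Individual safety rules.** In Table 2 (Section 4.2.1), the LDH row halts treatment, reassesses after two weeks, and then says "If within normal range, continue to treat at reduced dose, defined as the next lower dose". The haemoglobin and reticulocyte rows do the same in similar words. Other rows require discontinuation, or a halt followed by contact with the Medical Monitor.

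**Extension dose.** Section 4.2 says "Subjects participating in the Open-Label Extension will be switched over to the highest safest dose of the CCX140-B". Section 4 describes the open-label dose as "currently planned to be 15 mg twice daily", decided by the sponsor with DMC advice. Section 6.3.2 gives the same plan and allows the open-label dose to be lowered if it proves too high. SAP 3.5.1 sets the open-label trough-sampling window on the footing that every subject takes 15 mg twice daily.

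**Stopped subjects.** Section 4 says "All subjects who discontinue treatment will remain in the study for follow up and outcome recording", and Section 5.5 keeps them on the regular visit schedule.

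**The concern.** Table 2 decides dose for one subject on that subject's laboratory results. The extension text decides dose for everyone at once. Nothing connects the two, so a subject already reduced reaches Week 12 with two instructions that cannot both be followed.

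The events concerned are possible signs of haemolysis, which Section 4 treats as of special interest, and Section 2.4 expects the red-cell findings in animals to carry over to humans. Two sites could handle identical subjects differently and each be following the protocol.

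There is also a cost to the analysis. SAP 3.2.4 defines Safety_B as everyone dosed in the open-label period, with no marker for an earlier reduction or stop. SAP 3.4.1 summarises open-label UPCR change from Week 12 by prior treatment group. Most of Group D would have no dose change at Week 12, but a reduced Group D subject returned to 15 mg twice daily would have an increase and would be averaged with the rest.

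**Working it through.** The plan gives no figure on this point, so the check is a comparison of passages plus simple dose arithmetic.

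**Step 1. Sort the Table 2 rows by response.**

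| Response | Events | Rows |
|---|---|---|
| Discontinue | creatinine, UPCR, four ALT/AST rows | 6 |
| Halt, then next lower dose if recovered | LDH, haemoglobin, reticulocytes | 3 |
| Halt, then contact Medical Monitor | neuropathy, other significant events | 2 |

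Total: 6 + 3 + 2 = 11. None of the 11 appears among the three entry conditions.

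**Step 2. Follow a dose-reduced subject (3 of 11 rows).** The subject is on treatment at Week 12, has not withdrawn consent, has no precluding infection and needs no new immunosuppressive, so all three conditions are met. Table 2 says to continue at the lower dose and sets no end. Sections 4, 4.2 and 6.3.2 assign the common open-label dose. No passage carries an individual reduction into the extension or says that it lapses at Week 12.

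**Step 3. Size of the conflict, from the Table 1 regimens.**

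- 15 mg twice daily: 2 × 15 = 30 mg/day
- 10 mg twice daily: 2 × 10 = 20 mg/day
- 5 mg once daily: 5 mg/day
- Reduced from 15 to 10 mg twice daily, then extension: 30 / 20 = 1.5-fold
- Reduced from 10 mg twice daily to 5 mg once daily, then extension: 30 / 5 = 6-fold

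The 6-fold step is also what every Group B subject entering the extension is planned to take, so its size is not peculiar to this gap. What is peculiar is that the reduced subject was lowered for an individual safety event.

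**Step 4. Does the sponsor and DMC decision resolve it?** Section 6.3.2 adjusts one open-label dose for the study, and the DMC step-down in Section 4.2 applies to a whole arm. If 15 mg twice daily stays acceptable overall, the reduced subject's position is unchanged.

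**Step 5. Follow a stopped or held subject.** Sections 4 and 5.5 keep a stopped subject in follow-up, so that subject attends Week 12. Sections 5.4 and 7.7 do not say whether a Table 2 stop or an open hold bars entry. For stopped subjects, other text points against entry. Table 2 orders discontinuation of CCX140-B itself, the drug used in the extension, and gives no route to restart. Section 4 removes confirmed renal deterioration from the treatment phase, and it describes extension subjects as people continuing dosing.

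**The case against.** The strongest reply is that entry is not automatic. Section 5.4 is permissive, footnote 6 sets a floor, Section 5.5.2 lets the investigator or sponsor stop study drug for the subject's interest or safety, and Section 5.5 asks for Medical Monitor contact when a subject discontinues. The dose wording is qualified by tolerability and safety, Section 6.1 allows fewer tablets, and Section 4.2.1 gives the DMC the task of implementing the dose modification guidelines. Its charter is not among the documents.

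This stands as far as it goes, and it matters for stopped subjects. A reader might infer that someone stopped for a confirmed liver event qualifies at Week 12, or that the checklist overrides the stop. The documents do not support that: silence in 5.4 does not cancel an order to discontinue, and a permissive criterion overrides nothing.

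It does not answer the dose-reduced case. These are general powers; none is an entry condition and none sets the entry dose for someone already reduced. Section 6.5.3 also keeps investigators blinded to assignment until database lock, so at Week 12 the investigator cannot know how large the switch is.

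It is also fair to say that affected subjects are not invisible. Protocol 9.3.4 lists total and average daily dose, SAP 3.3.7 reports exposure duration by period, and SAP 3.6.1 lists events leading to discontinuation. A reader could piece the history together, but no planned summary separates these subjects.

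**Conclusion.** For subjects dose-reduced after an LDH, haemoglobin or reticulocyte event, the protocol contradicts itself on the open-label dose, and the SAP adopts one side. The clearest case is a return from 20 to 30 mg/day, 1.5-fold. For subjects stopped or on hold, the finding is only that 5.4 and 7.7 are silent and need aligning with the rest.

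The conclusion assumes that a Table 2 reduction outlasts Week 12, because no end is stated. If it was meant to lapse there, the protocol needs to say so. Frequency is unknown, since the documents give no event rate. The stated margin between projected exposure at 15 mg twice daily and the rat no-effect level (3-fold in Section 6.4, about 3- to 4-fold in Section 2.4) is context and not a measure of risk to such a subject. This should be fixed: it touches an individual safety decision and is cheap to correct, but it does not undermine the 12-week primary comparison.

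**What to change.** Reconcile Protocol 5.4, the Week 12 checklist in 7.7, footnote 6, Sections 4, 4.2 and 6.3.2, and SAP 3.5.1 with Table 2. A subject who has been reduced, is on hold, or was stopped under Table 2 should get one consistent answer on whether to enter and at what dose. Which rule applies is for the sponsor and DMC to decide. In the SAP, add a flag for these subjects in the Safety_B summaries and the open-label UPCR summaries.

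The cost is short edits in those places and to the Week 12 eligibility form. A few subjects may not enter, or may enter on a different dose. If the chosen rule lets anyone take less than 15 mg twice daily, two SAP details need to follow. The trough window in 3.5.1 is fixed at ±3 hours for all on the basis of twice-daily dosing. The compliance formula in 3.3.7 divides by 6 per day, so a fully adherent subject on, for example, 10 mg twice daily as open-label 5 mg tablets (4 per day) would score 4 / 6 = 67% and fall in the category below 80%.

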5.5. Removal of Subjects from Therapy of Assessment

Investigators must clearly distinguish between study drug treatment discontinuation and study withdrawal. Subjects who discontinue study drug treatment or who initiate medication changes (including those prohibited by the protocol) will not be automatically withdrawn from the study, but all efforts must be made to continue to follow the subjects for all regularly scheduled visits. The Medical Monitor should be contacted to determine how to address the specific situation.

Investigators must take appropriate measures to make sure that subjects are motivated to comply with all requirements of the protocol in order to minimize the amount of missing data. Subjects who discontinue study treatment early or initiate medication changes (including those prohibited by the protocol) should continue to be followed for all regularly scheduled visits for safety and efficacy assessments. Investigators and their staff must take measures to actively maintain contact with their subjects in the study, such as telephone calls, texts, or emails between visits, and offers for transportation support to visit the study site.

5.5.1. Subjects may be withdrawn from the study for the following reasons:

1. Subject withdrawal of consent to contribute additional outcome information;
2. Subject non-compliance with dosing or diary completion;
3. Loss to follow-up;
4. Sponsor's decision to terminate the study.

5.5.2. Subjects may discontinue study drug treatment for any of the following reasons:

1. Subject withdrawal of consent;
2. The Investigator may discontinue study drug treatment if, in his/her clinical judgment, it is in the best interest of the subject;
3. The Sponsor may request discontinuation of study drug treatment for safety reasons or non-compliance with treatment;
4. The Sponsor may request discontinuation of study drug treatment due to new or increased glucocorticoid/immunosuppressant treatment.

In the event of early withdrawal from the study, the tests and evaluations listed for the Early Termination visit in [Section 7.14](#) will be performed, whenever possible. Data collected at this visit will be designated as an "Early Termination" visit in the EDC. The Sponsor should be notified of all study drug treatment and study withdrawals in a timely manner.

If the Investigator considers a change in background treatment for FSGS, this should be discussed with the Medical Monitor, and decision made regarding discontinuation of blinded

study drug. Independent of continuation or discontinuation of study drug, subjects should continue in the study for assessment of outcome.

6. STUDY MEDICATION/TREATMENT

6.1. Product Characteristics

The investigational medicinal products (IMP) are oral film coated tablets containing 5 mg of CCX140-B and matching placebos. The tablets are manufactured under current good manufacturing practice. The clinical trial material is packaged in high density polyethylene (HDPE) bottles containing 30 tablets of either placebo or active. These bottles will be packaged in kits to administer to subjects in a blinded fashion; placebo, 5 mg once daily, 10 mg twice daily, and 15 mg twice daily.

During the blinded portion of the study, study drug will be supplied to each subject in kits. Each kit contains 3 bottles labeled with a yellow band for use in the morning and 3 bottles labeled with a blue band for use in the evening. Each bottle will be also labeled with a distinguishing number. Subjects will be instructed to take one tablet from each of the three yellow banded bottles in the morning, and one tablet from each of the three blue banded bottles in the evening.

During the open label phase of the study CCX140-B will be administered as up to 3 tablets (5 mg each) twice daily, depending on determination of the highest safest dose. During study weeks 13 through 24, distinction between morning and evening doses and bottles are not required since each bottle will contain active study medication at the same dose. Therefore the bottles dispensed for this phase of the study will neither include yellow or blue markings or distinct numbers.

6.2. Randomization and Method of Treatment Assignment

Eligible subjects will be enrolled and stratified based on two stratification factors: UPCR <3.5 g protein/g creatinine at baseline versus UPCR ≥3.5 g protein/g creatinine at baseline, and on glucocorticoid/immunosuppressives or no glucocorticoid/ immunosuppressives, and randomized to one of the four treatment groups in a ratio of 1:1:1:1; placebo: 5 mg CCX140-B QD:10 mg CCX140-B BID: 15 mg CCX140-B BID. Randomization will be performed centrally via an interactive response technology (IRT) system and minimization algorithm, using the stratification factors. In order to protect the blinding, the randomization schedule will not be accessible to study personnel who have contact with study centers or who are involved in data management and analysis.

